6.0 STUDY CONDUCT

Refer to the Schedule of Events ([Table 1](#)) for the list of study procedures/assessments to be conducted at each visit.

Data should be entered into the eCRF as soon as possible, preferably within 72 hours of collection from each subject.

6.1 Study Subject Number

Subject Number – assigned upon Screening examination.

Randomization Number – assigned by IWRS upon randomization of a subject on POD1.

Bottle Number – associated with the Randomization Number, assigned by IWRS.

If a subject requires a replacement study drug bottle, then a replacement Bottle Number will be identified through IWRS.

6.2 Description of Study Visits

6.2.1 Visit 1 - Screening

The Screening visit should occur no more than 28 days and no less than one (1) day prior to surgery. After obtaining written informed consent and HIPAA authorization, site staff will perform the assessments as shown in the Schedule of Events ([Table 1](#)). All ocular assessments must be performed on both eyes at the Screening visit.

If surgery is not performed on the planned scheduled day such that screening procedures would fall outside of the 28 day screening window, site staff must contact the Study Medical Monitor to determine which, if any, of the screening procedures must be repeated.

Subjects may be rescreened, if, in the opinion of the Investigator, the subject would qualify for the study if a procedure/assessment is repeated/redone (in this case, the subject keeps the same subject number). *Note: If subject who has failed screening is rescreened at a later time, the subject will be assigned a new subject number.*

Subjects who sign the informed consent form (ICF) and have undergone study procedures/assessments, but do not meet eligibility criteria any time prior to randomization on POD1 will be considered as screen failures. Limited information on screen failures will be transcribed to the eCRF.

After the screening assessments and before surgery, the subject may have a pre-surgery medical assessment to determine whether the subject is a suitable candidate for surgery. At this time, the

routine medication list prescribed by the cataract surgeon should be reviewed to rule out prohibited medications ([Table 4, Section 5.4.2](#)).

6.2.2 Day of Surgery (Day 0)

Prior to surgery, the surgeon's routine medication list should be reviewed to exclude prohibited medications ([Table 4, Section 5.4.2](#)). Surgery should preferably be scheduled in the morning to accommodate BID dosing on POD1. However, if surgery has to be scheduled in the afternoon, subjects should still instill two doses of study drug on POD1 at least 6 hours apart.

On Day 0, the surgeon will perform his/her routine cataract surgical procedure using phacoemulsification and implantation of a posterior chamber intraocular lens in the operated eye following the surgeon's usual pre-operative, operative, and post-operative procedures (with the exception of avoiding use of prohibited medications). Aqueous release procedures are not permitted.

Following surgery, the following should be performed:

- Give the subject instructions regarding routine post-surgical care and instructions regarding the use of concomitant medications and restricted medications during the study.
- Record surgery parameters (surgery time, phacoemulsion energy and an assessment of surgery difficulty) in the source documents and eCRF.
- Record the medications routinely administered for cataract surgery in the source documents. These medications will be reported as being used for routine cataract surgery.
- If a medication is administered due to an AE, the medication must be entered in the source documents, indicating that the medication was used to treat an AE.
- If a non-prostaglandin medication is used to lower IOP, the medication must be entered in the source documents and in the ConMeds page of the eCRF.
- AEs and ConMeds associated with an AE should only be recorded in the source document on Day 0 if they result in screen failure of the subject. If a subject is not a screen failure on Day 0, the AEs and ConMeds applicable to Day 0 should be recorded in the source documents when the subject returns for Visit 2 on POD1.
- Only for subjects who are randomized, enter the medications routinely used for cataract surgery and concomitant medications in the ConMeds page of the eCRF and AEs in the AE page of the eCRF.
- Schedule the subject to return to the clinic on the following day, ie., POD1, in the morning (if possible).

6.2.3 Visit 2 - POD1 (Day of Randomization)

Subjects will return to the clinic for the study visit on POD1 between 18 to 34 hours following conclusion of surgery on Day 0. This visit should be scheduled in the morning, as much as

possible, to allow for administration of two doses of study drug during the day on POD1 for randomized subjects. However, if surgery is to be performed in the afternoon, subjects should still instill two doses of study drug on POD1 at least 6 hours apart.

All assessments will be performed as shown in the Schedule of Events ([Table 1](#)). Ocular assessments will be performed only on the operated, study eye.

The site will review eligibility criteria ([Section 4.2](#) and [Section 4.3](#)) to determine if the subject qualifies for randomization. If the subject meets all criteria, the subject will be randomized by site personnel using the EDC/IWRS system. The site should follow the instructions provided in the Study Reference Manual)/eCRF Completion Guidelines to enter appropriate subject data into the eCRF and randomize the subject. A study drug bottle number will be assigned to the subject based on the predetermined randomization by the EDC/IWRS system. The designated site personnel should supervise the administration of the first dose of study drug by the subject in the clinic before dispensing the assigned study drug bottle along with written dosing instructions and diary to the subject. The second dose will be administered at home.

A subject who fails to qualify for the study on POD1 will not be rescreened.

Note that the use of IOP-lowering medications or aqueous release procedures are not allowed on POD1.

Study drug dosing/administration procedures including handling bottle replacement, diary/dosing compliance and the list of treatments are presented in [Section 5.1.2](#). Subjects are reminded to bring the diary to each clinic visit in order for site staff to review dosing compliance.

6.2.4 Visit 3 (POD4 ± 1) and Visit 4 (POD8 ± 1)

All assessments will be performed as shown in the Schedule of Events ([Table 1](#)).

Ocular assessments will be performed only on the operated, study eye at Visit 3 (POD4) and Visit 4 (POD8).

6.2.5 Day of Subject Contact on POD14

POD14 is the last day of dosing. Site personnel will contact the subject on POD14 (no specific window) to remind the subject not to take study drug on POD15 and onward and to bring the bottle of study drug and diary back to the clinical site at Visit 5 (POD15). Site personnel will contact the subject using the subject's preferred reliable method of communication, e.g., telephone call, cell phone text or email. The site staff must make an effort to ensure that the subject receives and acknowledges the receipt of the message. Method of contact and whether or not the subject was reached is to be documented in the source document.

Any AEs reported to the site during the POD14 contact must be recorded in the source documents and eCRF. Further assessment of any reported AEs may require an Unscheduled Visit on POD14 if medically significant or they may be assessed, as appropriate, at Visit 5 (POD15).

6.2.6 Visit 5 (POD15 + 1)

All assessments will be performed as shown in the Schedule of Events ([Table 1](#)).

Ocular assessments will be performed only on the operated, study eye.

Study drug bottle and final diaries will be collected at this visit.

6.2.7 Visit 6 (POD22 ± 2)

This is the final visit for the subjects.

All assessments will be performed as shown in the Schedule of Events ([Table 1](#)).

Ocular assessments will be performed on both eyes.

Subjects with ongoing AEs or SAEs should be handled as discussed in [Section 8.0](#).

6.2.8 Early Termination/Withdrawal

Subjects who are terminated/withdrawn from the study early will have the Visit 6 (POD22) assessments and a urine pregnancy test performed at the time of early termination, or as soon thereafter as possible. At an Early Termination/Withdrawal visit the ocular assessments are to be performed on both eyes.

[Appendix A](#) describes the Early Termination/Withdrawal procedures that may be implemented because of the COVID-19 pandemic.

6.2.9 Unscheduled Visits

Any visits performed beyond those specified within the protocol must be documented in the Unscheduled Visit pages of the eCRF. Unscheduled visits may include, but are not limited to, reporting and/or follow-up of AEs/SAEs, changes in concomitant medications, follow-up of subjects receiving rescue or IOP-lowering medications or ophthalmic assessments as deemed appropriate by the Investigator.

6.2.10 Study Visit Schedule for Rescued Subjects

Subjects who are rescued as discussed in [Section 9.4](#) will discontinue study drug and receive rescue medication.

The Investigator should make every effort to keep subjects who are rescued in the study until they complete the Visit 6 (POD22) assessments ([Table 1](#)).

6.3 Subject Early Termination (Withdrawal)

Any subject who wishes to voluntarily discontinue study drug or withdraw from participation in the study for any reason is entitled to do so without obligation. If a subject requests to discontinue the study drug, the subject will be withdrawn from the study as an Early Termination (see [Section 6.2.7](#)).

The Investigator may discontinue any subject from study drug or from study participation, if deemed necessary at any time during the study for any reason including, but not limited to:

- The investigator considers that the subject requires alternative medication that is incompatible with further continuation of the study drug or participation in the study.
- Occurrence of any medical condition or circumstance that exposes the subject to substantial risk and/or does not allow the subject to adhere to the requirements of the protocol.
- Any SAE, clinically significant AE, severe laboratory abnormality, intercurrent illness, or other medical condition that indicates to the Investigator that continued participation in the study is not in the best interest of the subject or that continued participation could affect study objectives.
- Any woman who reports becoming pregnant while participating in the study. Information on the pregnancy and outcome will be requested by the Investigator.
- Subject's continued failure to comply with protocol requirements or study-related procedures after being instructed on the correct requirements or procedures by the Investigator or site personnel.
- Termination of the study by the Sponsor, FDA, or other regulatory authority.

In the event that early termination/withdrawal of a randomized subject is necessary ('withdrawn' subject), the Investigator should make every attempt to complete the Visit 6 assessments and perform a urine pregnancy test as soon as possible ([Table 1](#)). Note: the Visit 6 ocular assessments need to be performed on both eyes.

The reason for early termination/withdrawal of a subject should be recorded in the source documents and entered in the eCRF.

Subjects who are terminated early from the study will not be replaced.

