9.4.2 Management

Investigators will use clinical judgment to determine when to rescue a subject using the guidance provided in [Section 9.4.1](#) and the appropriate rescue medication to use. All rescued subjects will stop study drug at the time of rescue and will continue in the study through completion of the Visit 6 (POD22) assessments ([Table 1](#)).

If a subject needs to be rescued at Visit 5 (POD15), the Visit 5 (POD15) assessments ([Table 1](#)) should be completed before the subject is administered rescue medication.

Rescued subjects will be considered treatment failures, and the need for rescue medication will not be considered as an AE.

An AE occurring at the time of rescue will be recorded in the eCRF and will be followed by the Investigator to stabilization or resolution of the AE or the end of the study (whichever comes last).

If a subject is rescued, this event will be recorded in the eCRF (not as an AE). Medications used for rescue will be recorded in the ConMeds section of the eCRF, indicating that they were used for rescue.

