9.5.2 Management

Investigator will use clinical judgment to determine the appropriate IOP-lowering medication to use and when to withdraw study drug and procedures, in consultation with the Study Medical Monitor.

It is important to note that prostaglandin-based IOP lowering medications are prohibited in this study.

- After randomization and start of study drug, if a subject has an IOP > 30 mmHg the Investigator may commence non-prostaglandin-based IOP-lowering medication while continuing the study drug, with appropriate follow-up at the next planned visit or at an unscheduled visit. The subject may require assessment at an unscheduled visit at the investigator's discretion.
 - If the IOP is < 30 mmHg at the next visit, the subject may continue on study drug.
 - If at the next visit, the IOP remains > 30 mmHg while on IOP-lowering medication, then the study drug may be discontinued and alternative IOP-lowering medication may be started, after consultation with the Study Medical Monitor. The subject should continue in the study and complete the assessments indicated in [Table 1](#) through Visit 6 (POD22). The Study Medical Monitor should discuss the persistent elevation of IOP with the Sponsor Medical Monitor.
- After randomization and start of study drug, an IOP of ≥ 21 mmHg **AND** an increase > 10 mmHg from the Visit 2 (POD1)/pre-dose baseline (both criteria must be met) is considered clinically significant and the Investigator should consider starting non-prostaglandin-based IOP-lowering medication while continuing the study drug, with appropriate follow-up at the next planned visit or at an unscheduled visit.
 - If the IOP reduction is satisfactory at the next visit, the subject may continue on study drug.
 - If the IOP reduction of IOP is not satisfactory at the next visit, then the study drug may be discontinued and alternative IOP-lowering medication may be started, after consultation with the Study Medical Monitor. The subject should continue in the study and complete the assessments indicated in [Table 1](#) through Visit 6 (POD22). The Study Medical Monitor should discuss the persistent elevation of IOP with the Sponsor Medical Monitor.

Medications used for treating increased IOP will be recorded in the Concomitant Medications section of the eCRF, noting that they were used to reduce IOP.

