6.3.4 Study Day and End of Study (EOS)

Study Day for each subject is calculated relative to the date of the first dose of study drug:

- Study Day = Visit Date/Event Date - Date of First Dose +1
When the Visit Date/Event Date is on or after the Date of First Dose
- Study Day = Visit Date/Event Date - Date of First Dose
When the Visit Date/Event Date is prior to the Date of First Dose

Study Day will be used to define analysis windows for efficacy analyses and to evaluate the timing of events or measurements occurring relative to the first dose of study drug.

Study Day ‘-1’ corresponds to Surgery Day 0 and Study Days ‘-29’ to ‘-2’ correspond to Screening Visit (Days -28 to -1) as shown in the Schedule of Events ([Table 2](#)).

EOS is defined as the last visit in the study. EOS will be either Visit 6/POD22 for subjects who complete the study or the Early Termination/Withdrawal visit for subjects who discontinue the study prior to Visit 6/POD22.

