6.3.5 Analysis Visit for Efficacy Analyses

The use of efficacy data collected in the study will be maximized by including the assessments that are performed outside the planned visit window. Each Analysis Visit (POD 4, 8 and 15) will use an analysis window to determine the efficacy data that will be used to derive the efficacy endpoints. The actual Study Day ([Section 6.3.4](#)) will be used to define the analysis window. The analysis window for each Analysis Visit is shown in Table 3.

Table 3: Analysis Windows for Efficacy Analysis

Analysis Visit	POD4	POD8	POD15
Study Days in Analysis Window	2 – 6	7 – 11	12 – 17 or Scheduled Visit*

* Only for subjects who (i) complete at least 14 days of dosing, (ii) do not use rescue medication and (iii) have a scheduled POD15 visit after Study Day 17

If the efficacy assessments are performed at unscheduled visits occurring after Visit 2/POD1 and before Visit 5/POD15, the date of the unscheduled visits will also be used to determine the appropriate analysis window.

The efficacy assessments performed after two days following the last dose of study drug will not be used when the subjects have administered less than 14 days of study drug.

When multiple efficacy assessments fall within the same analysis window for an Analysis Visit (see [Table 3](#)), the following rules will be applied:

- If two scheduled assessments fall within the same analysis window for an Analysis Visit and one of the Analysis Visits (either before or after the Analysis Visit with two scheduled assessments) has no scheduled assessment, then the scheduled assessment data will be used for the Analysis Visit without an assessment. For example, when a subject has a scheduled POD4 visit at Study Day 3 and a scheduled POD8 visit at Study Day 6, the Analysis Visit POD4 would have two scheduled assessments and the Analysis Visit POD8 would have no data. In this case, the scheduled POD8 visit assessments will be used for the Analysis Visit POD 8.
- If one scheduled assessment and at least one unscheduled assessment fall within the same analysis window for an Analysis Visit, the latest value in the analysis window will be used for all relevant efficacy analyses.

The definition of the Analysis Visit for the efficacy analyses will be re-examined prior to database lock. If there is a need to adjust the analysis window in Table 3, the SAP will be amended to document the changes.

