6.4.3 Handling Dropouts or Missing Data

6.4.3.1 Imputation of Missing Efficacy Data

The missing data handling rule for the study eye will be applied for the efficacy endpoints.

Missing data from subjects who discontinue the study before POD15 assessments without taking rescue medication:

For subjects who prematurely discontinue the study without taking rescue medication, the LOCF approach will be used to impute the missing data. The last observation will be the last assessment value after the first dose of study drug and up to two days following the last dose of study drug.

Missing data from subjects who discontinue the study and take rescue medication before POD15 assessments:

For both categorical and continuous secondary efficacy endpoints of ACC grade, ocular pain grade and ACF grade, subjects who take rescue medication before POD15 assessments and prematurely discontinue the study, the LOCF approach will be used to impute the missing data. The last observation will be the last assessment value after the first dose of study drug and prior to starting rescue medication.

Intermittent missing data:

The likelihood of having intermittent missing data is low. For subjects with intermittent missing data for efficacy endpoints, the LOCF approach will be applied to impute the missing data, i.e., using the data collected from the most recent prior visit after the first dose of study drug.

If no data can be carried forward (i.e., missing assessments at POD 4 visit or no available post-baseline assessments), missing data will be treated as missing for the continuous endpoints and will be considered as 'Non-responder' for the categorical endpoints.

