10.1.4 Additional Analysis

The primary efficacy endpoints will be analyzed using the data collected up to POD15. The rescued subjects will not be considered as treatment failures (Non-responders) for this analysis. All subjects' data collected up to POD15, including the data from subjects who take rescue medication, will be used to analyze the primary efficacy endpoints. Only observed data will be included to derive the primary efficacy endpoints. For the primary endpoint of ACC grade, subjects who miss one of POD 8 and POD15 assessments will be considered as treatment failures (Non-responders). For the primary endpoint of ocular pain grade, subjects who miss one of PODs 4, 8 and 15 assessments will be considered as treatment failures (Non-responders). The Pearson's Chi-square test will be used to test the treatment difference.

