11.2 Adverse Events

Non-serious AEs occurring from the start of study drug administration until EOS will be reported in the eCRF. Serious AEs (SAEs) occurring after signing the informed consent form until EOS will be reported in the eCRF. All AEs will be coded using MedDRA version 23.1 - September 2020, and classified by SOC and preferred term.

All AEs occurring from the start of study drug administration through the last day of participation in the study (EOS) are considered as TEAEs.

An overall TEAE summary by treatment group will be presented by the number of events and the number and percentage of subjects experiencing one or more events, including all TEAEs, treatment-related TEAEs, treatment-emergent SAEs, severe TEAEs, TEAEs leading to discontinuation, and death.

The number and percent of subjects reporting one or more TEAEs and the number of TEAEs will be tabulated by SOC, preferred term, and treatment group for all TEAEs. Results will be displayed in order of decreasing frequency based on the occurrence rate in the APP13007 group,

both across SOC and within each SOC term. Summaries of all ocular TEAEs, ocular TEAEs in the study eye, ocular TEAEs in the non-study eye, all non-ocular TEAEs, TEAEs related to study drug, ocular TEAEs related to study drug in the study eye, non-ocular TEAEs related to study drug, treatment-emergent SAEs, SAEs related to study drug and TEAEs leading to study discontinuation will also be presented in the same manner. The number and percent of subjects reporting one or more TEAEs will also be summarized by maximum severity for all TEAEs, ocular TEAEs in the study eye and non-ocular TEAEs.

The relationship of TEAEs will be determined by the relationship to study drug and/or to the ocular surgical procedure. Ocular TEAEs related to both study drug and surgery or related to surgery only will be summarized separately.

In addition, the incidence of TEAEs occurring in at least 5% of subjects in any treatment group and incidence of non-serious TEAEs above the threshold of 5% of subjects in any treatment group (for data transparency reporting) will be presented.

For summaries by severity of TEAEs, the most severe occurrence for a particular preferred term will be used for a given subject. AEs with missing severity will be considered as ‘Severe’ events for summary purposes, but will be presented as missing in the AE listings.

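### A subject who asks only to stop study drug is withdrawn from the study, so later visits are lost to the SAP 10.1.4 analysis and to serial safety follow-up

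*Protocol*

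**What the plan says.** Protocol 6.3 first treats stopping drug and withdrawing from participation as separate rights of the subject, then merges them: "If a subject requests to discontinue the study drug, the subject will be withdrawn from the study as an Early Termination". Under Protocol 6.2.8 such a subject has the Visit 6 assessments once, at termination or as soon after it as possible.

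Two other groups who stop drug are kept:

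- **Rescued subjects** (Protocol 9.4.2; also 5.4.1, 6.2.10 and 9.1.1.1): "All rescued subjects will stop study drug at the time of rescue and will continue in the study" to Visit 6.
- **Subjects whose IOP stays high on treatment** (Protocol 9.5.2): drug may be stopped, but "The subject should continue in the study and complete the assessments indicated in" Table 1 through Visit 6.

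On the analysis side:

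- **SAP 6.3.5:** when dosing lasted under 14 days, "The efficacy assessments performed after two days following the last dose of study drug will not be used". SAP 6.4.3.1 applies the same limit to the value carried forward for non-rescued dropouts: "up to two days following the last dose of study drug".
- **SAP 10.1.4:** all observed data to POD15 are used, including data after rescue, and rescue is not counted as failure. For ACC, "subjects who miss one of POD 8 and POD15 assessments will be considered as treatment failures (Non-responders"). For pain, a missing POD4, POD8 or POD15 value has the same result.
- **SAP 6.3.4:** for early leavers, end of study is "the Early Termination/Withdrawal visit for subjects who discontinue the study prior to Visit 6/POD22".
- **SAP 11.2:** "All AEs occurring from the start of study drug administration through the last day of participation in the study (EOS) are considered as TEAEs".

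**The concern.** These are different groups, so the protocol does not contradict itself. It does have an inconsistent retention policy. The sponsor already plans off-drug follow-up to POD22 for two groups of drug-stoppers and gives it up for a third without stating a reason.

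SAP 10.1.4 is the only planned analysis of the primary endpoints that can use outcomes from more than two days after drug is stopped. A rescued subject who attends contributes what was observed. A subject who asked to stop contributes an assigned failure, because the protocol ended the visits. The resulting bias can go either way, depending on which arm loses more subjects.

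For safety, IOP elevation is a named class risk. IOP and visual acuity after rescue are excluded from the study-eye summary tables (SAP 11.3.1 and 11.3.2), so rescued subjects' later visits cannot fill the gap there. A non-rescued subject kept on schedule off drug would contribute to those tables.

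**Working it through.** **1. What happens to the visits.** The first dose is on POD1, so Study Day 1 is POD1 (SAP 6.3.4). The analysis windows in SAP Table 3 are Study Days 2–6 (POD4), 7–11 (POD8) and 12–17 (POD15). The effect depends on when the termination examination falls:

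- Days 2–6: no POD8 or POD15 value, so non-responder on both endpoints in 10.1.4.
- Days 7–11: no POD15 value, so non-responder on both.
- Days 12–17: a POD15 value may exist, so no failure need be forced.

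**2. Why the primary analysis is untouched.** Visits more than two days after the last dose are already excluded by SAP 6.3.5 and 6.4.3.1. Keeping these subjects would not change their LOCF values.

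**3. Design figures** (Protocol 10.4). Inputs: 26% vs 12% (ACC), 57% vs 38% (pain), two-sided 5%, 175 per arm, 5% dropout. The formula is the pooled-variance chi-square without continuity correction:

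power = Φ{[Δ√n − 1.96√(2p̄(1−p̄))] / √[p₁(1−p₁)+p₂(1−p₂)]}.

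- ACC: (0.14×√175 − 1.96×√0.3078)/√0.298 = 1.40, power 91.9% (stated 92%).
- Pain: 94.8% (stated 95%).
- 175/0.95 gives 185 per arm.

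The plan's figures reproduce.

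**4. Shift in the 10.1.4 difference.** The documents do not say how many dropouts are subject-requested drug stops. The assumed range is 0 to 5% of 185 = 9.25, about 9 per arm. It is also assumed that the planned rates apply in 10.1.4 and that these subjects would have responded at those rates. Forcing k subjects in an arm to non-response lowers its rate from p to p(1 − k/185). For example, active k = 9 on ACC gives 0.26×176/185 − 0.12 = 0.1274.

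| Forced failures | ACC difference (points) | Pain difference (points) |
|---|---|---|
| None | 14.0 | 19.0 |
| 2, active only | 13.7 | 18.4 |
| 9, active only | 12.7 | 16.2 |
| 9, each arm | 13.3 | 18.1 |
| 9, placebo only | 14.6 | 20.8 |

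At 185 per arm, power in 10.1.4 with no loss is 93.3% (ACC) and 95.8% (pain). A 5% loss in both arms gives 91.7% and 94.0%. On active only it gives 88.7% and 87.9%; on placebo only, 95.3% and 98.3%.

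**5. Margin in the primary comparison.** Rounded expected responders are 48 vs 22 (ACC) and 105 vs 70 (pain), with Pearson p = 0.0006 and 0.0003. Switching 9 placebo non-responders to responders gives p = 0.031 and 0.007. Losing significance takes 11 switches for ACC (p = 0.059) and 17 for pain (p = 0.061).

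**6. Safety example.** A subject attends POD4, asks to stop and is examined on POD5. Of the four post-baseline scheduled visits (POD4, 8, 15, 22), three are not held, with one termination examination in their place. Under SAP 11.2 the TEAE window is POD1–POD5, 5 days, instead of about 22.

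**The case against.** The strongest reply is that few subjects fall under this rule. Lack of efficacy, or pain or photophobia that persists or worsens, can lead to rescue. Persistent IOP elevation has its own route, and Protocol 6.3 lets the investigator end drug or participation separately. What remains is a subject's own request outside those routes, so taking the whole 5% dropout is an upper limit, not an estimate. This stands. So does the point that people who quit treatment may not respond at the planned rate, which would make the active-arm shifts smaller. On the other side, Protocol 9.1.1.3 and 9.1.1.4 let the investigator stop drug and withdraw the subject, so the gap is not confined to subject requests.

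Second, 10.1.4 is a supplementary analysis outside the fixed sequence and the listed sensitivity analyses, and its missing-visit rule applies to everyone. That limits the stakes. It does not explain why the protocol should create the missing visits.

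Third, the SAP change may look redundant. Rescued subjects are off drug, so the promise to use their data already implies that the two-day exclusion is lifted. That is the better reading, but 10.1.4 does not say so, and applying 6.3.5 literally would discard most post-rescue data as well.

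Fourth, safety follow-up is reduced, not removed. The termination visit is a full examination of both eyes and fills the end-of-study rows. Unresolved AEs are followed where possible (Protocol 8.4), and Protocol 8.1.1 words the TEAE window as running through POD22. All of this is right, but the POD8 and POD15 rows stay empty for an early stopper, and the end-of-study row holds an earlier value.

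**Conclusion.** The point holds, as an improvement worth considering rather than a flaw that threatens the trial. Protocol 6.3 ends visits for a group whose off-drug outcomes SAP 10.1.4 is built to use, and 10.1.4 then counts the absence as failure. At most about 9 subjects per arm are affected, on the assumption that every planned dropout is of this kind. The 10.1.4 difference then moves by at most 1.3 points for ACC (14.0 to 12.7) and 2.8 for pain (19.0 to 16.2), when all the loss is on active. Power falls by under 2 points if the loss is balanced, and by about 5 (ACC) and 8 (pain) points if it is all on active. These figures assume response at the planned rates. The primary LOCF conclusion does not depend on 6.3. The safety loss is limited to serial off-drug observation in the subjects who stop.

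**What to change.** - **Protocol 6.3:** state that a subject who stops study drug continues the scheduled visits through POD22 unless the subject also declines follow-up. The right to withdraw fully is unchanged. Keep an examination at the time of stopping, so that the on-drug value for LOCF is not lost. In the same edit, correct the cross-reference from 6.2.7 to 6.2.8.
- **SAP 10.1.4:** state that the two-day off-drug exclusion in 6.3.5 does not apply to this analysis.

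The primary LOCF analysis stays as planned. The safety tables need no new rule, because SAP 11 already summarizes observed data at scheduled visits. The cost is about one sentence in each document, some visits that are already in the schedule, and a small amount of off-drug data to handle.
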